# **List of Abbreviations**

Term	Definition		
CDC	Centers for Disease Control and Prevention		
CI	Confidence interval		
HIPAA	Health Insurance Portability and Accountability Act		
ICD-10-CM	International Classification of Diseases, Tenth Revision, Clinical Modification		
ICD-9-CM	International Classification of Diseases, Ninth Revision, Clinical Modification		
ICD-O-3	International Classification of Diseases for Oncology, Third revision		
IMS	IMS Health		
IRR	Incidence rate ratio		
LRx	IMS longitudinal prescription database		
MSA	Metropolitan Statistical Area		
NDC	National Drug Code		
US	United States		

### 3. Observational Research Protocol

### 3.1. Rationale

Forteo (teriparatide) was initially approved in 2002 in the United States (US) for the treatment of postmenopausal women with osteoporosis at high risk for bone fractures and for increasing bone mass in men with primary or hypogonadal osteoporosis who are at high risk for fracture. In 2009, the treatment indication was expanded to include treatment of men and women with glucocorticoid-induced osteoporosis who are at high risk for fracture.

In rats, in one 2-year (near-lifetime) toxicology study in which doses were administered at levels that produced systemic exposures 3 to 60 times greater than that of a 20- $\mu$ g dose in humans, teriparatide caused increases in bone mass and a dose-dependent increase in the incidence of osteosarcoma, a malignant tumor (Vahle et al. 2002; Forteo USPI 2012). A subsequent rat study conducted to determine the effect of duration of treatment and age at initiation of treatment found that the bone neoplastic response in rats was dependent on both dose and duration of treatment. The study established a "no-effect" dose of 5  $\mu$ g/kg when initiated at 6 months of age, and continued for a duration of either 6 months or 20 months (Vahle et al. 2004). In a long-term study of cynomolgus monkeys (spanning 18 months of treatment plus 3 years of follow-up observation), no bone tumors were detected by radiographic or histological evaluation (Vahle et al. 2008). Studies have shown that the rat skeleton is more sensitive than monkey or human skeletons to the pharmacological effects of parathyroid hormone in the formation of new bone and osteosarcomas (Miller 2008).

Osteosarcoma has rarely been reported in people who have received treatment with Forteo. It is not known if patients who are treated with Forteo have a higher risk of osteosarcoma; however, there have been spontaneous reports of osteosarcoma in Forteo-treated patients.

In 2009, a prospective US Forteo Patient Registry study addendum (Study GHBX[2]), was added as a component of the Forteo Post-Approval Osteosarcoma Surveillance Study (GHBX). This study addendum included a prospective voluntary registry of patients treated with Forteo to complement the US and European retrospective components of the GHBX study. The Forteo Patient Registry is a voluntary prospective cohort study with a 1-time registration of consenting adult patients (aged ≥18 years) living in the US who have received treatment with Forteo. Data from the registered patients are linked to participating state cancer registry data to ascertain any new confirmed cases of osteosarcoma. The objective of the Forteo Patient Registry study is to estimate the incidence of osteosarcoma in patients who have received treatment with Forteo. To achieve this objective, the registry target is to observe 1.7 million patient-years within the study population. Based on current enrollment estimates/projections, the registry will need to continue at least through 2024 to meet this objective.

The 2 retrospective components of the GHBX studies include a US case finding study as well as a case finding study in the European Union. The US case finding study is ongoing. The European component of the GHBX surveillance studies was a 10-year safety surveillance study to evaluate a potential association between Forteo and adult osteosarcoma in humans. The study

included 5 Nordic countries (Denmark, Finland, Iceland, Norway, and Sweden) with national registries and used a case-series design to identify incident cases of osteosarcoma from participating cancer registries. This study completed in 2014 and found that none of the patients diagnosed with osteosarcoma in the study had prior Forteo exposure.

This database study will add to the scientific information generated to date by using a commercial pharmacy claims database to identify Forteo-treated patients and linking with data from participating state cancer registries. This database study analyzing outpatient pharmacy claims will be conducted in parallel with a second database study analyzing Medicare data. Analysis of each of these data sources will be conducted independently using harmonized protocols and customized statistical analysis plans based on the unique features of each data source. It is expected that the 2 aforementioned data sources will serve as a more efficient approach (versus the existing model involving voluntary patient recruitment) in identifying patients exposed to Forteo, and for subsequent linkage to the US cancer registries. As a result, we anticipate achieving our stated objective (estimating the incidence of osteosarcoma among Forteo users) sooner than the currently estimated Forteo Patient Registry 2024 timeframe.

Claims databases provide longitudinal data capture, which is useful in assessing rare events such as osteosarcoma, given the need for a large population, and allows for more precision and increased accuracy to assess this potential risk (Schneeweiss and Avorn 2005). Large pharmacy claims data can be representative and are often used to describe drug utilization patterns for the general population, including special populations like the elderly, which is a population more likely to be treated with Forteo (Schneeweiss and Avorn 2005; Bradley et al. 2007). Claims databases include an accurate record of dispensing dates, and are not biased by knowledge of the study outcome, which allows for an inclusive picture of the use of certain drugs in a population and its dynamics, making this the gold standard for drug exposure information (Schneeweiss and Avorn 2005).

At least annually, an existing advisory board provides a comprehensive review of GHBX study data, spontaneous reports, and any relevant information in the published literature on Forteo treatment and osteosarcoma in humans, in order to advise whether there is a possible signal of increased risk and to recommend additional follow-up activities. The progress and results of the database linkage studies will be included in the advisory board review.

Following assessment of the findings from the linkage and the overall progress of the GHBX surveillance program in 2016, Lilly will consult with the regulators, where appropriate, to decide whether the strength of the evidence is sufficient or whether a further linkage is required.

# 3.2. Objectives

# 3.2.1. Primary Objective(s)

To estimate the incidence of osteosarcoma in patients who have received treatment with Forteo over time as compared to a general population comparator cohort using an incidence rate ratio (IRR) and 95% confidence interval (CI).

# 3.2.2. Secondary Objective(s)

To characterize the Forteo user and comparator cohort using the following:

- Demographic characteristics
- Select prescription drugs dispensed during the baseline period
- Duration of Forteo use for Forteo-treated cohort
- Provider specialty

### 3.2.2.1. Optional Secondary Objective

To assess the similarity of the Forteo cohort and the comparator cohorts using medical claims for the following factors measured during the baseline period:

- History of radiation treatment
- History of fracture
- History of cancer
- History of Paget's disease of the bone
- Number of inpatient and outpatient visits within the prior 4 months
- History of chronic comorbid conditions using available data

### 3.3. Research Design

This cohort study will estimate the incidence rate and IRR for osteosarcoma among adult patients aged ≥18 years treated with Forteo compared to an untreated population. Drug exposure data will be obtained from dispensed pharmacy claims and osteosarcoma diagnosis information will be obtained from state cancer registry files. Study cohorts created in the commercial claims database will be linked to state cancer registry data to assess whether or not they have been diagnosed with osteosarcoma using predefined oncology codes.

# 3.3.1. Study Type

This is an observational database study using a matched cohort design. The study cohorts will include patients aged ≥18 years with a pharmacy-dispensed prescription of Forteo compared to 2 unexposed cohorts. The first unexposed cohort will include any patients not treated with Forteo. The second will include any patients treated with osteoporosis medications other than Forteo. Each Forteo user will be matched to a target of 2 patients from the unexposed osteoporosis cohort and 4 patients from the unexposed general population cohort on demographic variables, payer type, time of entry into the cohort (month and year), and a count of therapeutic classes dispensed.

This study will link the commercial pharmacy claims database (IMS longitudinal prescription [LRx] database) containing drug exposure information to state cancer registry databases containing osteosarcoma diagnosis information. In addition, an optional sensitivity analysis has been planned which links commercial medical claims database (IMS PharMetrics database) to evaluate baseline patient characteristics.

### 3.3.2. Data Sources

### IMS Longitudinal Prescription (LRx) Data

The IMS Health (IMS) longitudinal prescription database (LRx) consists of patient-level dispensed prescriptions that enable patient prescription-filling behavior to be tracked across time, payers, and pharmacies. Data contributors include retail chains and independent pharmacies, specialty, mail-order, and long-term care pharmacies. The LRx captures prescriptions purchased through all methods of payment (for example, cash, Medicaid, third party). Currently, the database contains data for over 220 million unique de-identified patients and 1 million physicians. Data are consistently robust across all regions of the country, ranging from 57% coverage in the Southwest to 70% to 80% in the Mid-Atlantic region. The LRx represents >85% of all US retail prescriptions and 40% to 75% of US specialty and mail-order prescriptions (depending on therapeutic area). The IMS documents the saturation of pharmacies in LRx at the state and the Metropolitan Statistical Area (MSA) level; these internal IMS data can be used to estimate data completeness. The LRx data are available from 2005.

The database includes de-identified patient-level longitudinal data such as age, sex, zip codes, dispensed drug (through National Drug Code [NDC]), molecule, form, strength, quantity, and days' supply. All data are Health Insurance Portability and Accountability Act (HIPAA) compliant to protect patient privacy.

There are limitations to using pharmacy claims data for research purposes. Claims data are generated primarily for reimbursement purposes and not research. One such limitation is potential misclassification given that exposure is identified based on a claim for a dispensed prescription without information that confirms whether or not the patient actually used the medication. Based on market research data, 70% of new patients refill their Forteo prescription at least once, and 64% refill their prescription to cover at least 90 days. Therefore, the potential for exposure misclassification is likely to be minimal. In addition, LRx is an open source claims database with data contributed by pharmacies, not health plans. As such, the completeness of data capture is contingent upon the consistency of data contributions from pharmacies.

The patient counts for Forteo from LRx are as follows:

• IMS Longitudinal Prescription (LRx) Data (January 2005 to January 2016): 477,140 patients, with approximately 23,000 patients with a prescription filled in 2015.

### **State Cancer Registry Databases**

State cancer registry databases will be used to identify osteosarcoma cases diagnosed in the US during the years of observation. The variables of interest include demographic variables for matching and osteosarcoma diagnosis codes (See Table 1 in Attachment 1), month and year of diagnoses, and other clinical and pathological information. (See Section 3.5.2 for additional variables needed for linkage prior to analysis.) All US state cancer registries will be contacted with the target to recruit at least 25 state registries for participation in linkages. Results from an initial feasibility survey sent to 41 state cancer registries suggest that at least 60% are willing and able to participate in this effort. The recruitment and coordination with state registries will be handled within a parallel research study, under the facilitation of RTI Health Solutions.

Because of the lack of detailed, clinical diagnosis information in claims data, which use International Classification of Diseases diagnosis codes (ICD-9 and ICD-10), state cancer registries are deemed the appropriate source for osteosarcoma diagnosis information using International Classification of Diseases for Oncology, Third revision, (ICD-O-3) codes. State cancer registry data include information on cancer histology, stage at diagnosis, tumor grade, and date of diagnosis.

### IMS PharMetrics PlusTM Database

The IMS PharMetrics PlusTM database is the largest claims database of integrated medical claims in the US. The aggregated IMS PharMetrics Plus database comprises adjudicated claims for more than 150 million unique enrollees across the US. Enrollees with both medical and pharmacy coverage represent 100 million lives. Data are available from 2006 onwards; with a typical 4-month lag due to claims adjudication. PharMetrics Plus includes a diverse representation of geography, employers, payers, providers, and therapy areas, with the majority of 3-digit zip codes in the US covered and reported. Patients in the PharMetrics Plus database are similar to the national, commercially insured population in terms of age and sex for individuals aged 65 and under. Although there is representation of individuals aged 65+, this is an underrepresentation relative to the overall US population. The 65 and older population will be assessed in a parallel study using Medicare claims.

### PharMetrics Plus contains:

- Inpatient and outpatient diagnoses (International Classification of Diseases, 9th Revision, Clinical Modification [ICD-9-CM] codes; International Classification of Diseases, 10th Revision, Clinical Modification [ICD-10-CM] codes).
- Inpatient and outpatient procedures (Current Procedural Terminology, 4th Edition, Healthcare Common Procedure Coding System, and ICD-9-CM codes), other data elements including dates of service, demographic variables (for example, age, sex, and geographic region), and start and stop dates of health plan enrollment.

Data contributions are subjected to a series of quality checks to ensure a standardized format and to minimize error rates. All data are HIPAA compliant to protect patient privacy. PharMetrics Plus data used for this study will be limited to medical claims to assess baseline patient characteristics for a sensitivity analysis.

The linkage rate between the LRx database and PharMetrics Plus for this patient population is expected to be very low due to the age distribution of Forteo users and the underrepresentation of the 65 and older patient population. In addition, PharMetrics Plus data are available from 2006 forward. Initial estimates suggest 4% of Forteo users in LRx can be linked to enrollees with both medical and pharmacy coverage in PharMetrics Plus. However, enrollees with medical coverage, regardless of pharmacy coverage, will be eligible for linkage. This data source has been included as an optional sensitivity analysis.

### 3.3.3. Study Populations

Patient eligibility for inclusion in the study cohorts

Forteo-treated Patients:

• This group includes patients with at least 1 prescription for Forteo.

### Matched Comparators:

- General population: This group includes patients with a dispensed prescription for any other medication, other than Forteo.
- Osteoporosis population: This group includes patients with a dispensed prescription, other than Forteo, for treatment of osteoporosis.

### 3.3.3.1. Forteo-Treated Patients

Patients treated with Forteo will be identified in the pharmacy claims database using dispensed prescriptions of Forteo identified by NDCs (See Table 2 in Attachment 1). This design improves the accuracy of drug exposure information by eliminating recall bias. One or more dispensed prescriptions of Forteo during the study period will qualify patients as Forteo-exposed. This study design will include both prevalent and new users. If a patient in the comparator cohort receives a prescription for Forteo during the observation period, the person-time will be censored from the comparator cohort on the date of the prescription for Forteo, and subsequent person-time will be counted in the Forteo cohort. Given the limited use of Forteo, this would be expected to rarely occur.

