### 3.3.4.2. Linkage

The linkage will include a cohort of Forteo users and matched comparators with qualifying dispensed pharmacy claims from 01 January 2005 through December 2 years prior to the linkage year. A deterministic data linkage method will be used to match on demographic variables across the commercial claims study cohorts and cancer registry data. The state cancer registry data will extend through December 2 years prior to the linkage year to account for the 9- to 18-month lag in data collection and reporting among state cancer registries in the year of the linkage. The index date will be the date of the earliest identified dispensed prescription for Forteo and the comparators will have a dispensed prescription during the same calendar month and year.

For optional sensitivity analyses, an attempt will be made to link all study cohorts to the PharMetrics Plus database for ascertainment of medical claims representing baseline patient characteristics. The linkage rate between the LRx database and PharMetrics Plus for this patient population is expected to be very low due to the age distribution of Forteo users and the underrepresentation of the 65 and older patient population.

Analysis will be conducted looking at 2 time periods. The first time period will include all exposure and outcome data from 01 January 2005 through December 2 years prior to the linkage year. This second time period will include a baseline look-back period of at least 3 months prior to the cohort entry date and will include the 6-month lag time. The baseline period will be used to identify descriptive characteristics used for matching for each cohort.

The risk detection window will be the period of time after the index date up until the linkage completion date. Person-time will be calculated for Forteo-treated population and comparator cohorts, and an IRR for the occurrence of osteosarcoma will be calculated to compare the 2 cohorts.

A follow-up linkage, if required, will be a replication of the methods and inclusion/exclusion criteria of the first linkage.

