All US state cancer registries will be invited to participate; however, it is expected that not all state registries will participate. As a result, the participating state cancer registries will cover only a percentage of the US population aged ≥18 years during the observation period. This will be addressed in 2 ways: 1) calculation of incidence rates and IRRs using a cohort restricted to patients in states with participating registries; 2) using a coverage fraction that represents the percentage of osteosarcoma cases captured in this study (based on cancer registry participation) divided by the total number of osteosarcoma cases expected. This will involve a recalculation of the person-time at risk using the exposure information for only those patients from the states with participating registries and comparing it with the proposed person-time calculation using the coverage fraction to see if they differ in a meaningful way, and repeating the IRR analysis for comparison with the IRR analysis not using the coverage fraction.

The observation period, or the time at risk, will be defined as the time postentry into the study cohort. Person-time will be calculated from the start of the observation period until the end of the study period, the linkage date, which will then be mortality adjusted and multiplied by the coverage fraction based on the participating registries. For patients with an osteosarcoma diagnosis, the observation period will begin the day after the index date and will end at the date of osteosarcoma diagnosis rather than the linkage date.

Cohorts will be selected prior to linking to registry data. If a Forteo-exposed patient is identified as having a registry identified diagnosis of osteosarcoma prior to the index date, this patient as well as their matched comparators will be removed from the study. If a Forteo-matched comparator is identified as having a registry identified diagnosis of osteosarcoma prior to the

index date, the comparator alone will be dropped from the analysis and a substitute comparator will be selected.

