Descriptive characteristics will be reported for both the Forteo-exposed and comparator cohorts (See Table 1). Among the Forteo cohort, drug utilization patterns will be reported including the number of dispensed prescriptions, mean days of supply, dosage form and strength. Baseline characteristics will be reported in total and stratified by reporting age categories. The number and percent of patients along with descriptive statistics (mean, standard deviation, median, 25th and 75th percentiles) will be reported for continuous data. Categorical variables (for example, payer type) will report the number and percent of patients. Baseline characteristics reported in Table 1 will be summarized for both cohorts.

Two time periods are included with variable look-back windows for assessment of osteosarcoma diagnosis postcohort entry using a data-driven approach. Additionally, 2 comparator cohorts will be established and analyzed. The analysis will be conducted using the following scenarios:

- Primary time period: Using the full 10 years of data available for Forteo exposure and the matched cohort. This will be January 2005 through December 2 years prior to the linkage. State cancer registry data will be linked to all data during this window. This approach assesses all available data and provides a more comprehensive analysis.
- Secondary time period: Using a data-driven approach, a sensitivity analysis will be conducted. This sensitivity analysis will include a variable look-back window where the exposed cohort will only be included when at least a 3-month look-back period is available prior to the index date to describe baseline characteristics.

Findings from these analyses will be described and compared.

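### The protocol's refill figures do not support calling exposure misclassification minimal, and no planned IRR would show whether the ever-dispensed rule dilutes the result

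*Protocol*

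**What the plan says.** - **Exposure rule.** Protocol 3.3.3.1: "One or more dispensed prescriptions of Forteo during the study period will qualify patients as Forteo-exposed". The cohort takes both prevalent and new users.
- **Time at risk.** Section 3.4.1: "The observation period, or the time at risk, will be defined as the time postentry into the study cohort". Section 3.3.4.2: "The risk detection window will be the period of time after the index date up until the linkage completion date". For cases, follow-up ends at diagnosis. Nothing ends exposed time when the drug is stopped. The primary time period is described as "Using the full 10 years of data available for Forteo exposure and the matched cohort".
- **Refill evidence.** Section 3.3.2 (LRx data) names the problem that "exposure is identified based on a claim for a dispensed prescription without information that confirms whether or not the patient actually used the medication". It then cites market research that "70% of new patients refill their Forteo prescription at least once, and 64% refill their prescription to cover at least 90 days" and concludes: "Therefore, the potential for exposure misclassification is likely to be minimal".
- **Rationale.** Section 3.1 reports that "the bone neoplastic response in rats was dependent on both dose and duration of treatment". It gives no duration threshold for humans.
- **Duration in the analysis.** Duration of use is a secondary objective for describing the cohort (3.2.2), and drug utilization is reported descriptively (3.4.1). Section 3.4.4 plans no subgroups. Section 3.4.6 mentions a cumulative-exposure assessment in a missing-data rule, but no IRR is attached to it.

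**The concern.** Section 3.3.2 uses refilling as its evidence that dispensed drug was taken. By the same reasoning, three in ten new patients supply no such evidence, and more than a third do not reach 90 days' cover. A conclusion of minimal misclassification does not follow from those proportions.

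The exposure rule then carries any such problem through the whole follow-up. A patient with one fill early in the window contributes exposed time for up to about ten years, and 90 days is about 2.5% of ten years (90 / 3652.5). If short use carries less risk than sustained use, mixing the two pulls the IRR toward 1.

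In a safety study that matters most when the result is null, because the reader cannot tell absence of risk from risk confined to longer users. The other planned IRRs do not help. The osteoporosis comparator, 6-month lag, differential mortality, coverage fraction and look-back analyses all keep the ever-dispensed rule. Section 3.4 also makes data-driven sensitivity analyses depend on the number of cases, so a near-null result could reduce the scrutiny it receives.

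**Working it through.** **The protocol's own figures.** The 70% and 64% are source figures, so there is no derivation to reproduce. Their complements are:

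- no refill: 1 − 0.70 = 0.30
- less than 90 days' cover: 1 − 0.64 = 0.36

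The two groups overlap, since patients who never refill should fall largely or wholly among those below 90 days. The figures are therefore alternatives and must not be added.

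**Dilution formula.** Let R be the true IRR in longer users, f the share of exposed person-time held by short users, and s the fraction of the excess risk that short users carry.

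Observed IRR = (1 − f)·R + f·[1 + s·(R − 1)] = 1 + (R − 1)·[1 − f·(1 − s)]

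**Assumptions, none of which the protocol supplies.** R and s are chosen for illustration. f is set to 0.30 or 0.36 by treating shares of new patients as shares of person-time. That requires follow-up to be equal whatever the duration of use.

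| True IRR | f = 0.30, s = 0 | f = 0.36, s = 0 | f = 0.30, s = 0.5 | f = 0.36, s = 0.5 | s = 1 |
|---|---|---|---|---|---|
| 1 | 1.00 | 1.00 | 1.00 | 1.00 | 1.00 |
| 2 | 1.70 | 1.64 | 1.85 | 1.82 | 2.00 |
| 3 | 2.40 | 2.28 | 2.70 | 2.64 | 3.00 |
| 5 | 3.80 | 3.56 | 4.40 | 4.28 | 5.00 |

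For example, with R = 3, f = 0.36 and s = 0: 1 + 2 × 0.64 = 2.28. With s = 0.5: 1 + 2 × 0.82 = 2.64.

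The loss of excess is therefore 30% or 36% when short users carry none of it, 15% or 18% when they carry half, and nil when risk does not depend on duration. At a true IRR of 1 nothing changes.

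**What this could mean for information.** The Schoenfeld approximation is used here, with an exposed share of 0.2 (1:4 matching), two-sided alpha 0.05 and an assumed 80% power. Events needed at a true IRR of 2 rise from 103 to 175 (f = 0.30) or 201 (f = 0.36), both with s = 0. At a true IRR of 3 they rise from 41 to 65 or 73. The planned analysis is exact conditional Poisson regression, and the readable text states no target IRR or power. These counts show scale only and are no finding about the study's power.

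**The case against.** The strongest reply is that ever-dispensed is the right definition for the question asked. The primary objective concerns patients who have received Forteo. For a cancer outcome, carrying exposure forward is reasonable if any use can confer lasting risk. A patient who filled once and took the drug is correctly classified as ever-exposed. Section 3.3.2 means dispensed but not used, not short use, and 3.4.3 already lists that limitation. This stands, and it is why the primary analysis should not change.

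A reader might infer that 30% or 36% of the cohort is misclassified. The documents do not support that. Failure to refill is only indirect evidence of non-use, so these are upper-end proxies. They are also shares of patients rather than person-time, and they come from new patients while the cohort includes prevalent users.

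A reader might also infer that the IRR is in fact diluted. That would require short users to carry less excess risk. Section 3.1 shows duration dependence in rats only, notes that the rat skeleton is more sensitive than the human one, and says it is not known whether treated patients have a higher risk.

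Finally, it can be said that the cumulative-exposure assessment in 3.4.6 may be developed in a SAP, and that making sensitivity analyses depend on case numbers was deliberate. Both are fair. Neither repairs the inference in 3.3.2, and the protocol itself attaches no IRR to duration.

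**Conclusion.** The point holds in conditional form. The conclusion that misclassification is minimal is not supported by the figures offered for it. One dispensing makes all later person-time exposed in every planned IRR, so if risk needs sustained use the reported IRRs may understate it, and no IRR defined in the protocol would reveal this.

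Under the upper-end assumptions in the table, up to 30% to 36% of the excess IRR would be lost, about half that if short users carry half the excess, and none if risk does not depend on duration. The actual share of short users in this mixed cohort is unknown. The documents therefore support saying that dilution is possible, not that it occurs, and they give no estimate of its actual size.

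**What to change.** 1. Keep the ever-dispensed analysis as primary.
2. In 3.3.2, remove the conclusion that misclassification is minimal. State that the ever-exposed IRR may understate risk if risk requires sustained use.
3. Prespecify two supporting IRRs that do not depend on the number of cases. In one, exposed person-time starts at the second dispensing. In the other, it starts when cumulative supply reaches 90 days. Restart each user's matched comparators at the same elapsed time from index, so that no immortal time is created.

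Fill dates, days of supply and quantity are already study variables (Table 1 in 3.3.5), so no new data are needed. The costs are two extra reruns, less exposed person-time and wider intervals. Some sustained users may be lost because LRx did not capture their refills: 3.3.2 describes an open source whose completeness depends on pharmacy contributions, with 40% to 75% capture of specialty and mail-order prescriptions. Under the missing-data rule in 3.4.6, patients with invalid supply data would drop out of the 90-day version. These limits are acceptable in supporting analyses and should be stated alongside them.
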